- Post-treatment safety follow-up: 10-14 days following study completion of the treatment period or premature discontinuation

The randomisation scheme will be stratified by co-variates for age (2 yrs - 9 yrs, 10 yrs - 17 yrs) and sex (M/F). A minimum of 18 subjects must be recruited into each age group with 25% of either sex.

A maximum of 12 subjects will be recruited in the 1 months to < 2 years age group and they will only be assigned to ferric maltol. Once there is evidence of metabolism and elimination of maltol from Pre-assignment PK samples, they will continue to the Treatment Phase and be assigned to the ferric maltol arm. Subjects will be eligible to enter the treatment phase if their maltol level returns to baseline, or to a level confirming there is no accumulation of maltol or maltol glucuronide.

Where applicable country and local regulations and infrastructure for home healthcare allow, home healthcare may take place at a location other than the clinical trial site to perform study

CONFIDENTIAL Page 43 of 80

assessments, which may include but are not limited to collection of blood and urine samples, measurement of vital signs, length/height, and weight.

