8.6 TREATMENT ASSIGNMENT AND BLINDING

At randomisation, the Interactive Response Technology (IRT) will assign children aged 2 yrs to 17 yrs to either the ferric maltol or ferrous sulfate treatment group. The site will dispense the appropriate number of open-label ferric maltol bottles or ferrous sulfate at each scheduled study visit according to the schedule of assessments. Study Treatment and duration is specified in section 5.5.2 of this protocol.

Children aged 1 m - < 2 yrs: all subjects will receive ferric maltol oral suspension following satisfactory completion of the pre-assignment phase.

This is an open label study and treatment assignment is not blinded.

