2 STUDY OVERVIEW

2.1 Study Objectives

2.1.1 Primary Objective

- To compare the safety and gastrointestinal tolerability of ferric maltol oral suspension and ferrous sulfate oral liquid in children and adolescents aged 2 years to 17 years, and assess the safety and tolerability of ferric maltol oral suspension in children 1 month to less than 2 years, in the treatment of iron deficiency anaemia during the 12 weeks treatment period.
- To assess the effect on haemoglobin (Hb) in children and adolescents aged 1 month to 17 years after twice daily ferric maltol oral suspension administration for 12 weeks.

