2.2.4 Sample Size Determination

In total up to 110 patients will be recruited into the study. Up to 98 subjects will be randomised in the 2 -17 years cohort and up to 12 subjects will be assigned in the <2 years cohort.

The aim is to recruit up to 49 subjects in each treatment group in the 2 – 17 years cohort. At least 12 subjects in each age group respectively (i.e. 24 subjects in total) will be included in the PK analysis group in the ferric maltol oral suspension group. A sample size of 49 in the Ferric Maltol group provides at least 80% power to demonstrate that the lower bound of the 95% confidence interval for increase in Hb at 12 weeks, compared with baseline, is above zero. This assumed that the standard deviation (SD) of the change from baseline is 1.2 g/dL or lower and the true mean change is at least 0.5 g/dL.

Every effort will be made to recruit up to 12 subjects in the under 2's age group but in case of reasons of feasibility it cannot be completed, then the study may be completed without that cohort.

If less than 91 subjects in total have been randomised when 32 ferric maltol subjects have completed treatment (or withdrawn from the study), then an interim analysis of the primary effectiveness endpoint (change in Hb concentration from baseline to Week 12) will be conducted. If significant, the study will stop recruitment. If not significant, the study will continue (all subjects will be assigned to ferric maltol) until 54 subjects have been recruited in the ferric maltol arm.

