3.2.3 Safety Population

The Safety Population is defined as all randomised/assigned subjects who receive at least one dose of study drug. All safety data will be analyzed using the Safety Population.

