3.3.8 Study Drug Exposure and Compliance

Days of exposure to study drug will be calculated as date of last dose of study drug – date of first dose of study drug + 1. For subjects who received a dose during the pre-screening period the date of first dose will be the date of first dose in the treatment phase. Note that the exposure calculation is intended to describe the length of time a subject was exposed to study drug and therefore does not take study drug interruptions into account. Days of exposure to study drug will be summarised by treatment based on the Safety Population with descriptive statistics and with counts and percentages of subjects with exposure in the following categories:

- <=6 days,
- 7 27 days,
- 28 55 days,
- 56 83 days,
- >= 84 days.

Days of exposure to study drug will be summarised separately for those who received a dose in the pre-assignment phase and those who didn't.

Percent compliance to the study drug regimen will be calculated as 100 x doses taken/ doses expected as recorded in dosing diary. Percent compliance to the study drug regimen will be summarised by treatment based on the Safety Population with descriptive statistics and with counts and percentages of subjects with compliance in the following categories:

- <80%,
- 80-120%,
- >120%.

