3.6 Safety Assessment

Safety data will be summarised by actual treatment received (and in total for selected analyses) based on the Safety Population.

Safety and gastrointestinal tolerability will be compared between ferric maltol oral suspension and ferrous sulfate oral liquid via the incidence of TEAEs, TESAEs and TEAEs leading to premature discontinuation of study drug, estimated as the number of subjects with at least one event divided by the number of subjects in the Safety Population.

Adverse Events (AEs) will be categorised by primary system organ class and MedDRA preferred term as coded using the MedDRA dictionary version 24.0. The number, intensity, relation to study medication and action taken will be described by incidence tables. Serious Adverse Events (SAEs) will be listed and tabulated separately.

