3.6.1 Adverse Events (AEs)

AEs will be captured from the date of informed consent through study completion (Follow-up visit). All AEs will be coded to system organ class and preferred term using MedDRA version 24.0. TEAEs are defined as AEs that start after the first dose of study drug.

An overview of AEs will be provided including counts and percentages of subjects (and event counts) with the following:

- Any AEs,
- Any TEAEs (overall and by maximum severity),
- Any study drug related TEAEs (overall and by maximum severity),
- Any SAEs,
- Any TESAEs,
- Any study drug related TESAEs,
- Any TEAEs leading to discontinuation of study drug,
- Any study drug-related TEAEs leading to discontinuation of study drug.
- Any AEs leading to death.

Counts and percentages of subjects (and event counts) will also be presented by system organ class and preferred term for each of the categories in the overview.

Listings will be presented specifically for SAEs and TEAEs leading to discontinuation of study drug.

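### SAP 3.6 compares adverse event incidence over the whole Safety Population, so up to 12 uncontrolled infants enter only the ferric maltol rate, although the primary objective compares the products in ages 2 to 17

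*SAP*

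**What the plan says.** **Objective.** SAP 2.1.1, like Protocol 6.1, sets ferric maltol against "ferrous sulfate oral liquid in children and adolescents aged 2 years to 17 years, and assess the safety and tolerability" of ferric maltol on its own in children younger than 2. The comparison is confined to ages 2 to 17, and the infant part is a single-arm assessment.

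**Who gets what.** Protocol 7.1 caps recruitment at 12 in the youngest "age group and they will only be assigned to ferric maltol". Protocol 8.6 says of these children that "all subjects will receive ferric maltol oral suspension following satisfactory completion of the pre-assignment phase". SAP 2.2.4 plans up to 98 randomised subjects aged 2 to 17, and "up to 12 subjects will be assigned in the <2 years cohort".

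**Analysis.** SAP 3.6 summarises safety by treatment received. It compares the products on the incidence of TEAEs, TESAEs and TEAEs leading to discontinuation, each "estimated as the number of subjects with at least one event divided by the number of subjects in the Safety Population". SAP 3.2.3 reads: "The Safety Population is defined as all randomised/assigned subjects who receive at least one dose of study drug". SAP 3.6.1 adds that "Counts and percentages of subjects (and event counts) will also be presented by system organ class and preferred term" for every line of the overview. Neither 3.6 nor 3.6.1 mentions an age restriction, an age split or a randomised-only table. Protocol 12.2.1 uses the same incidence rule and also sets no age limit.

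**Elsewhere in the SAP.** Demographics, medical history, medications and secondary endpoints are split by age (3.3.4 to 3.3.6, 3.4.2). Exposure is to be "summarised separately for those who received a dose in the pre-assignment phase" and for the rest. The Hb model has an additional analysis of randomised subjects only (3.4.1).

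**The concern.** The safety comparison is a primary endpoint, and it serves the only primary objective that sets one product against the other. Under the stated rule the ferric maltol rate mixes a randomised group aged 2 to 17 with infants who have no control, while the ferrous sulfate rate contains randomised subjects aged 2 to 17 only. Part of any difference in the table could then reflect age rather than product. Because no test is planned, the displayed rates are the whole result.

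The same issue would arise for older children if an interim analysis is held and is not significant. All later subjects are then assigned to ferric maltol (SAP 4.1) and would enter that rate without concurrent controls.

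**Working it through.** **Inputs.** 49 randomised per arm in ages 2 to 17 (SAP 2.2.2); at most 12 infants, all on ferric maltol (SAP 2.2.2, Protocol 7.1); total up to 110 (SAP 2.2.4). Everyone is taken to be dosed.

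**Plan's own total.** 2 × 49 + 12 = 110, as stated.

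**Denominators under SAP 3.6.** Ferric maltol 49 + 12 = 61; ferrous sulfate 49.

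**Infant share of the ferric maltol rate.** With k infants and r randomised ferric maltol subjects, the share is k/(k + r).
- Full recruitment, k = 12: 12/61 = 19.7%.
- Full recruitment, k = 6: 6/55 = 10.9%.
- Cohort dropped, which SAP 2.2.4 allows: 0%.
- Recruitment stopped after an interim, k = 12: the share rises as r falls. Examples are r = 45 (about half of 90 randomised), 12/57 = 21.1%; r = 32, 12/44 = 27.3%; r = 20, 12/32 = 37.5%. The last applies if infants count towards the 32 completers that trigger the interim. The documents do not say whether they do, so these are illustrations and not bounds.

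**Effect on the displayed difference.** Let p be the event rate in ages 2 to 17 on ferric maltol and q the rate in infants. The pooled rate is (49p + 12q)/61, so the shift is (12/61)(q − p).

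**Any TEAE.** The documents give no infant rate. The nearest figure is 20 of 37 subjects (54.1%) aged 10 to 17 in an earlier 10-day study (Protocol 5.4.3). The gap q − p is therefore an assumption:

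| Assumed gap, either direction | Shift (12/61 × gap) |
|---|---|
| 10 points | 2.0 points |
| 20 points | 3.9 points |
| 30 points | 5.9 points |

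A count example with no product difference in ages 2 to 17: let each randomised arm have 20/49 = 40.8%. If 8 of 12 infants have an event, ferric maltol shows 28/61 = 45.9%, which is 5.1 points higher. If 3 of 12 do, it shows 23/61 = 37.7%, which is 3.1 points lower. The shift is zero only if infants and older children have the same rate.

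**TESAEs and discontinuations.** In the same earlier study no subject had an SAE and 1 of 37 (2.7%) discontinued for a TEAE. At rates that low, an infant rate 10 to 30 points lower is impossible and an excess of that size has no support, so the table above does not apply. Counting works better here: each infant with an event adds 1/61 = 1.6 points to the ferric maltol rate. Infants without events dilute it slightly; at p = 2.7%, 12 event-free infants lower it by 12/61 × 2.7 = 0.5 points.

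**The case against.** The other side has several fair points.

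- **Safety analyses should count every dosed subject.** They still would. Infants stay in the Safety Population, and a column of their own also serves the second half of the objective.
- **The analysis is descriptive only (SAP 3.1.5).** This is correct. A reader might infer that type I error or power is compromised, but the documents do not support that, because no safety test is planned.
- **The objective already states the age limit, so the intention is clear.** The intention is clear, but SAP 3.6 sets an explicit denominator that departs from it.
- **Table layouts may be settled elsewhere.** SAP 6 refers to separate programming specifications, which are not among the documents, and promises subject listings. These may soften the problem. The denominator of a primary comparison is nevertheless fixed in the SAP text, and listings keep infants identifiable without giving the rate for ages 2 to 17.
- **The cohort may be small or absent.** This stands, and the effect shrinks with it. The rule still has to be set beforehand.
- **The Hb analysis is a weak precedent for redefining the comparison.** This also stands. SAP 3.4.1 pools assigned and randomised subjects in its main model and only adds a randomised-only analysis. By analogy alone, one would merely add a table. The case for making ages 2 to 17 the main comparison rests on the wording of the objective.

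**Conclusion.** The mismatch is certain from the text: the rule in SAP 3.6, followed as written, gives a ferric maltol rate for a different population from the one in the primary objective. At full recruitment with 12 infants, 19.7% of that denominator is uncontrolled infants.

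The consequence is less certain. The 2.0 to 5.9 point shift applies to any TEAE only, at full recruitment, and rests wholly on the assumed gap of 10 to 30 points. Three stronger readings are tempting but unsupported:
- that the infants favour or penalise ferric maltol: the direction is unknown, because no infant event rate is given;
- that the same shift applies to TESAEs and discontinuations: about 1.6 points per infant with an event is the appropriate scale there;
- that the infant share after an early stop can be capped: it would be larger than 19.7% with 12 infants and fewer than 49 randomised to ferric maltol, but the documents do not fix the counts.

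This should be fixed. Its weight is moderate, because the comparison is descriptive and the infant cohort may not be filled.

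**What to change.** In SAP 3.6, base the between-product comparison of TEAEs, TESAEs and TEAEs leading to discontinuation on randomised, dosed subjects aged 2 to 17. Keep infants, and any subjects assigned to ferric maltol after a non-significant interim, in the Safety Population, but show each group in its own column of the 3.6.1 tables. A pooled Safety Population total can stay as a supplementary display. Record the change in SAP section 5, because Protocol 12.2.1 sets no age limit.

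The cost is SAP wording, extra table columns and one entry in section 5, with no new data. The downside is a smaller ferric maltol denominator in the comparison, 49 instead of up to 61. One subject with an event then moves the rate by 1/49 = 2.0 points instead of 1/61 = 1.6.

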3.6.1 Adverse Events (AEs)

AEs will be captured from the date of informed consent through study completion (Follow-up visit). All AEs will be coded to system organ class and preferred term using MedDRA version 24.0. TEAEs are defined as AEs that start after the first dose of study drug.

An overview of AEs will be provided including counts and percentages of subjects (and event counts) with the following:

- Any AEs,
- Any TEAEs (overall and by maximum severity),
- Any study drug related TEAEs (overall and by maximum severity),
- Any SAEs,
- Any TESAEs,
- Any study drug related TESAEs,
- Any TEAEs leading to discontinuation of study drug,
- Any study drug-related TEAEs leading to discontinuation of study drug.
- Any AEs leading to death.

Counts and percentages of subjects (and event counts) will also be presented by system organ class and preferred term for each of the categories in the overview.

Listings will be presented specifically for SAEs and TEAEs leading to discontinuation of study drug.

3.6.2 Clinical Laboratory Tests

Clinical Chemistry and Haematology will be collected at the Screening Visit and Visit 6 (Day 84). In addition, Haematology will be collected at Visit 4 (Day 28) for those subjects in the 2-17 years of age group. Additionally, Hematology and iron markers will be collected at Visit 2 for the 1 month to < 2 years age group.

At Visit 7, Clinical Chemistry and Haematology will be collected if the subject has an ongoing AE that requires onsite assessment/management, or if the subject early discontinued.

Chemistry parameters include vitamin B12, folate, alanine aminotransferase (ALT), aspartate aminotransferase (AST), alkaline phosphatase (ALP), gamma-glutamyl transpeptidase (GGT), total bilirubin, creatinine, amylase, blood urea nitrogen (BUN), phosphorous, sodium, potassium, chloride, calcium, total cholesterol, uric acid, glucose, total protein, albumin.

Haematology parameters include red blood cell count, haemoglobin, haematocrit, mean cell volume (MCV), white blood cell count (total and differential (% and absolute)), absolute reticulocyte count and platelet count.

Descriptive statistics for each safety laboratory parameter will be presented for baseline values and for values and the change from baseline at each post-baseline visit.

Values outside the normal range will be categorised as below the lower limit of normal or above the upper limit of normal based on the central laboratory's normal reference range. Values

outside of the normal range will be summarised. Shifts from baseline to worst post-baseline category will be tabulated by laboratory parameter and shift category (low to low, normal to low, high to low, low to normal, normal to normal, high to normal, low to high, normal to high or high to high) for chemistry and haematology parameters.

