7.3.1 Inclusion Criteria

- 1. Patient is willing and able to comply with the study requirements and to provide written informed consent. In the case of patients under the age of legal consent, the legal guardian(s) must provide informed consent and the patient should provide assent per local and national requirements.
- 2. Age ≥1 month and ≤17 years at the time of informed consent
- 3. Subjects must have iron deficiency anaemia defined by the following criteria, as measured by the central laboratory at the screening visit

Haemoglobin thresholds define anaemia by age and gender:

- Children (1 m < 5 yrs) < 11.0 g/dl
- Children (5 yrs < 12 yrs) <11.5 g/dl
- Children (12 yrs) <12.0 g/dl
- Female child (≥13 yrs) <12.0 g/dl
- Male child (≥13 yrs) <13.0 g/dl

And

Ferritin thresholds define anaemia by:

- ferritin <30 μg/L,
- or ferritin <50 μg/L with transferrin saturation (TSAT) <20%,
- 4. Female subjects of childbearing potential must agree to use a highly effective method of contraception (which includes complete abstinence) until study completion and for at least 4 weeks following their final study visit. Highly effective contraception is defined as a method which results in a low failure rate, i.e., less than 1% per year when used consistently and correctly, such as implants, injectables, some intrauterine contraceptive devices (IUDs), a vasectomised partner and oral contraceptive medications.

The need for contraception and compliance with contraception requirements will be

CONFIDENTIAL Page 44 of 80

assessed at every visit for adolescent patients, and urine pregnancy testing will be performed at each visit for female subjects of childbearing potential.

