7.5 INDIVIDUAL DISCONTINUATION CRITERIA

Subjects and/or their parents or guardians have the right to withdraw consent without prejudice at any time during the study. If a subject withdraws consent, the Investigator should make a reasonable effort to determine the cause. All withdrawn subjects should have a Post-Treatment Safety Visit within 10-14 days after the last dose of study drug (if the subject agrees in the case of withdrawn consent).

If there is any sign of accumulation of maltol or glucuronide in the pre-assignment phase PK day for subject population aged 1 month to less than 2 years, the recruitment to this age group will be suspended and they will not enter the treatment phase until the risk has been assessed and approved via a substantial amendment to the protocol.

Subjects may be discontinued prematurely during the study for the following reasons:

- Withdrawal of informed consent
- A drop of >1 g/dl in Hb from baseline
- Unwillingness or inability to comply with protocol requirements
- Pregnancy or not using a reliable method of birth control (female subject of childbearing potential)
- Use of prohibited concomitant medications
- Serious adverse events that are judged by the Investigator to be related to study treatment

CONFIDENTIAL Page 47 of 80

- Blood transfusions for any cause during the study treatment period
- Use of any other single agent prescribed iron medications
- Occurrence of any condition that, in the opinion of the Investigator, significantly
 jeopardizes the wellbeing and safety of the patient, including any intolerable toxicity
 related to study treatment determined by the investigator to be unacceptable given
 the severity of the event

The reason for study drug discontinuation and the date of last dose should be recorded in the eCRF. Subjects who discontinue treatment prematurely must return for the Post-Treatment Safety Visit, unless informed consent is withdrawn (and the subject and/or their parents or guardians do not agree to attend this follow-up visit). A subject who meets discontinuation criteria should be discussed on an individual basis with the Medical Monitor.

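### The shift table to the worst post-baseline category puts children who correct after Day 28 in the same Hb cell as those who never correct, and compares two draws at ages 2-17 with one in infants (minor; confined to one descriptive safety table)

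*SAP*

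**What the plan says.** SAP 3.6.2 plans shift tables for chemistry and haematology: "Shifts from baseline to worst post-baseline category will be tabulated by laboratory parameter and shift category". Low, normal and high are "based on the central laboratory's normal reference range". The limits of that range are not given, and no direction is stated for what counts as worst.

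Haematology is scheduled for every child at Screening and Day 84. For the older children, "In addition, Haematology will be collected at Visit 4 (Day 28) for those subjects in the 2-17 years of age group". Infants have an extra draw at Visit 2, but it precedes assignment (SAP Table 2.2, notes) and so serves as baseline under SAP 3.1.3.

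Entry requires low Hb: "Subjects must have iron deficiency anaemia defined by the following criteria, as measured by the central laboratory at the screening visit". The cut-offs are fixed by age and sex, from 11.0 to 13.0 g/dl (Protocol 7.3.1).

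SAP 3.6 summarises safety data by treatment received and states no age split for the laboratory tables. Infants receive only ferric maltol (Protocol 7.1).

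Protocol 7.5 lists among the reasons for possible discontinuation: "A drop of >1 g/dl in Hb from baseline".

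**The concern.** A worst-value shift is built to catch children who start normal and become abnormal. For Hb in this trial the usual path should run the other way: low at entry, then rising over weeks. Under the rule, one low value at Day 28 fixes the child as *low to low*, whatever Day 84 shows.

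The rule also depends on how often a child is measured. Worst of two cannot look better than worst of one at the same response. Because the children with one scheduled post-baseline draw are all on ferric maltol, a table pooled by treatment would carry an artefact in that arm's favour.

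Two smaller gaps sit beside this. For parameters that can be abnormal in either direction, nothing says how to classify a child who was low once and high once. And no table counts children whose Hb fell by more than 1 g/dl, although the protocol singles out that fall. At stake is how one safety table reads.

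**Working it through.** The plan gives no figure for this table, so there is none to reproduce. Its only Hb sizing figure, at least 80% power with 49 children, SD 1.2 and mean change 0.5 g/dL, checks out (81.5% by noncentral t), but this point does not rest on it.

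**Step 1: what each pattern reads as.** Take a child aged 2-17 who is low at baseline, with low as the worse category.

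| Day 28 | Day 84 | Shift table shows |
|---|---|---|
| low | low | low to low |
| low | normal | low to low |
| normal | low | low to low |
| normal | normal | low to normal |

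An infant is classified by Day 84 alone.

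**Step 2: size.** Let p28 and p84 be the proportions normal at each draw. Assume that a child normal at Day 28 stays normal. Then:

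- *low to normal* at ages 2-17 = p28; in infants = p84
- share of corrected children read as *low to low* = (p84 − p28)/p84
- share of the *low to low* cell that is corrected = (p84 − p28)/(1 − p28)
- pooled ferric maltol = (49·p28 + 12·p84)/61, against p28 on ferrous sulfate
- spurious gap = (12/61)(p84 − p28)

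Inputs: 49 per arm and up to 12 infants (SAP 2.2.2). p84 = 65% is borrowed from the adult IBD study in Protocol 5.4.1 as an illustration. p28 is an assumption.

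| p28 | Corrected, read *low to low* | Corrected share of that cell | Ferric maltol, pooled | Ferrous sulfate | Gap (points) |
|---|---|---|---|---|---|
| 10% | 55/65 = 85% | 55/90 = 61% | 12.7/61 = 20.8% | 10% | 10.8 |
| 30% | 35/65 = 54% | 35/70 = 50% | 22.5/61 = 36.9% | 30% | 6.9 |
| 50% | 15/65 = 23% | 15/50 = 30% | 32.3/61 = 53.0% | 50% | 3.0 |

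With p84 anywhere from 50% to 80% and p28 from 10% to 50%, the misread share runs from 0% (p28 = p84) to 88%, and the gap from 0 to 13.8 points. If some children relapse, fewer than p28 are normal at both draws, so both effects grow.

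**Step 3: number of infants.** With 3 infants the multiplier is 3/52 instead of 12/61. At p28 = 30% the gap is (3/52) × 35 = 2.0 points. With none it is zero.

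**Step 4: the plan's own Hb assumptions.** A simulation used the SAP's SD of 1.2 g/dL at Day 84 and mean rises of 0.5 (the SAP value), 1.0 and 2.0. Also assumed: half the rise by Day 28 with SD 1.0, correlation 0.7, and starting deficits spread evenly over 0 to 2 g/dL. Relapse was allowed. Normal at Day 84 against normal at both draws was 35.4% v 20.2%, 49.9% v 28.9% and 77.2% v 48.0%. The misread shares are 43%, 42% and 38%. Multiplying the differences by 12/61 gives gaps of 3.0, 4.1 and 5.7 points.

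**Step 5: after the change.** Classified at Day 84 only, ages 2-17 and infants both read p84, so the age gap (15 to 55 points in the Step 2 table) and the pooled gap both become zero.

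**The case against.** The strongest reply is that the information is already planned elsewhere. SAP 3.6.2 also gives values and changes from baseline at each post-baseline visit. Hb change is a primary endpoint (SAP 3.4.1). Week 12 normalisation is a secondary endpoint on the same laboratory range, split by age group (SAP 3.4.2). A worst-value table is a common conservative safety display and answers a different question. All of this stands. A reader might infer that the shift table is uninformative, or that it contradicts the Week 12 endpoint. The documents support neither: the *low to normal* cell keeps information, *normal to low* still shows deterioration, and the two outputs differ by design.

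Further points also stand:

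- A fall from 10.5 to 8.5 g/dL is *low to low* in any reference-range shift table, so by-visit shifts alone would not reveal it.
- Low baseline Hb in the table is presumed. Entry uses protocol thresholds, the table uses a laboratory range with unstated limits, and nothing requires low haematocrit, red cell count or MCV.
- Twelve infants is a maximum, and SAP 2.2.4 allows completion without that cohort.
- Infants have one *scheduled* post-baseline haematology draw. SAP 3.6.2 allows a further one at Visit 7 after early discontinuation or for an ongoing event.
- In the middle case, 6.9 points is below one standard error: √(0.369 × 0.631/61 + 0.30 × 0.70/49) = 9.0 points. No test is planned on this table.

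The reply does not cover three things. The other outputs do not make this table comparable between arms, and they do not define worst. They also do not count children whose Hb fell. A by-visit minimum shows only the largest fall. Discontinuation reasons (SAP 3.3.1) miss children who stay on, since Protocol 7.5 makes discontinuation optional and discussed case by case.

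**Conclusion.** The point holds as a minor one. That late correctors share a cell with children who never corrected follows from the rule and the visit schedule, given a low baseline. How many are affected depends on assumed response rates.

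The tilt towards ferric maltol is conditional. It needs a table pooled across ages, infants enrolled, and more children normal at Day 84 than at both draws. Under the illustrated rates with 12 infants it is about 3 to 11 points. A reader might infer that the plan as a whole favours ferric maltol. It does not: the effect is confined to this descriptive table, the laboratory table layout by age is not stated, and no primary or secondary conclusion changes.

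The missing count of Hb falls above 1 g/dl is a separate omission and does not come from the worst-value rule. The undefined direction of worst matters for two-sided haematology parameters, and little for chemistry, which has one scheduled post-baseline draw.

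**What to change.** In SAP 3.6.2:

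- For Hb and, for consistency, haematocrit, red cell count and MCV, replace the shift to the worst value with shifts from baseline to Day 28 and from baseline to Day 84.
- Show infants separately from ages 2-17. Infants have no scheduled Day 28 column.
- Add one row, by arm and age group, counting children whose Hb was more than 1 g/dL below baseline at any post-baseline measurement. This reports an existing protocol criterion and changes no clinical rule.
- For the remaining haematology parameters, tabulate the lowest and the highest post-baseline category separately, which settles the direction of worst.

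The data are already collected. The cost is SAP wording, one re-specified table shell and slightly longer output.
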